### 2.1 STUDY RATIONALE

The anti-CD38 antibody isatuximab targets antibody-producing plasma cells, which express a high density of CD38. Isatuximab treatment may decrease anti-RBC autoantibody levels in individuals with wAIHA, thereby decreasing RBC destruction and increasing hemoglobin levels. The first part of this study will assess safety and determine the isatuximab dose for this patient population. The second part of the study will assess efficacy.

### 2.2 BACKGROUND

Among antibody-producing cells, plasma cells are unique in that they are long-lived (lifespan of months to years), reside primarily in the spleen, bone marrow, and inflamed tissue, and do not express CD20, the target of rituximab (2). Neither conventional immunosuppressive therapies nor rituximab deplete plasma cells. As a result, there has been significant interest in the use of anti-CD38 therapies in diseases in which antibodies play a significant role in pathogenesis. Currently there are 5 ongoing trials investigating anti-CD38 monoclonal antibodies for the treatment of autoimmune or antibody-mediated diseases. These diseases include: antibody-mediated rejection in the setting of kidney (NCT04294459) and heart (NCT04088903) transplantation, myasthenia gravis (NCT04159805), systemic lupus erythematosus (NCT03724916), and persistent primary immune thrombocytopenia (NCT04278924).

wAIHA is characterized by anti-RBC autoantibodies, which directly result in RBC destruction through Fc-related mechanisms such as antibody-dependent cell-mediated cytotoxicity (ADCC) or complement fixation. The diagnostic test for wAIHA is the direct Coombs test (also called the direct antiglobulin test (DAT)), which detects antibodies on the surface of RBCs. This test is positive in over 99% of wAIHA patients, as compared to less than 1% of the general population (4). The depletion of autoantibodies in wAIHA should therefore directly impact disease pathogenesis and result in improvement of anemia. In a Phase 3 clinical trial comparing the combination of rituximab and steroids to steroids alone, all participants who no longer harbored anti-RBC antibodies at Week 52 (as demonstrated by a negative DAT) also achieved a complete response (5).

First-line treatment for wAIHA is corticosteroids, which results in long-term remission in approximately 30% of patients (6). Rituximab is often introduced as second-line therapy. While approximately 85% of individuals with wAIHA respond to rituximab, with over 50% maintaining disease-free survival at 2 years (7), options are limited for those who do not. These patients typically undergo splenectomy or are treated with other immunosuppressive or cytotoxic agents such as cyclophosphamide, many of which have significant adverse effects. There has been accumulating evidence that patients with autoimmune hemolytic anemia who do not respond to rituximab have continued autoantibody production mediated by plasma cells. In wAIHA patients who failed to respond to rituximab and subsequently underwent splenectomy, plasma cells secreting anti-RBC autoantibodies were present in the spleen (8). The hypothesis that plasma cells are responsible for continued RBC destruction in patients who fail rituximab has been tested through the use of bortezomib, a proteasome inhibitor that causes apoptosis of plasma cells. In two case series, a total of 12 wAIHA patients who failed numerous therapies including rituximab were treated with bortezomib (9, 10). Overall, 9 of the 12 patients had a response to bortezomib (5 partial responses and 4 complete responses). Additionally, case reports describe the use of daratumumab, another anti-CD38 monoclonal antibody, in 4 patients with rituximab-refractory hemolytic anemia following hematopoietic stem cell transplantation (HSCT) (11, 12). These patients were treated with multiple therapies, including rituximab and bortezomib, but a sustained response was observed in 3 of the 4 patients only following daratumumab therapy. A case report also describes a wAIHA patient who responded to daratumumab after being refractory to azathioprine and rituximab (13). Thus, isatuximab represents a promising approach for the treatment of wAIHA, particularly for those patients who have previously failed prior therapies.

A detailed description of the chemistry and pharmacology of isatuximab, and its efficacy in the setting of RRMM and other hematological malignancies, is provided in the Investigator's Brochure and package insert.

## 2.3 BENEFIT/RISK ASSESSMENT

As of the cut-off date of 05 January 2020, it was estimated that approximately 1652 individuals have been treated with intravenous isatuximab in the setting of multiple myeloma and other malignancies, including various solid tumors. In general, isatuximab is well-tolerated. The most common adverse reactions for isatuximab are infusion reactions (IRs), which are clinically manageable.

Isatuximab has been investigated either as monotherapy or in combination with other anticancer agents in patients with hematological malignancies and other advanced malignancies. When isatuximab is given in combination with other anticancer agents, the overall safety profile of the combination appears consistent with the safety profile of each drug individually. The safety profile of isatuximab monotherapy has been assessed by a pooled analysis of monotherapy studies in 212 participants with multiple myeloma (TED10893 and TED14154). In these studies, the most common treatment emergent adverse events (TEAE), excluding the AEs corresponding to laboratory abnormalities, included IRs, fatigue, nausea, anemia, cough, upper respiratory infection, diarrhea, headache, and dyspnea. No safety data is available from healthy volunteers or non-oncology patient populations.

### 2.3.1 Infusion reactions

Infusion reactions occurred in 53.8% of the 212 participants assessed in studies TED10893 and TED14154. Almost all participants received pre-medication for infusion reactions. Approximately 98% of infusion reactions were Grade 1 or 2, with 2 Grade 3 and 6 Grade 4 reactions. There were no deaths. There was not a clear dose-response relationship for the incidence of IRs, but the incidence was higher at doses  $\geq 10$  mg/kg (56.8% of participants experienced an IR) than at doses  $< 10$  mg/kg (35.4% of participants experienced an IR). The majority of IRs occurred with the first infusion and all IRs were reported on the day of infusion. Among participants who received doses  $< 10$  mg/kg, no infusion reactions occurred after the second infusion.

The underlying mechanism of infusion reactions due to immune-cell directed monoclonal antibodies remains unclear, but these reactions appear to be reduced with subcutaneous administration (14). Approximately 50% of RRMM patients who receive intravenous daratumumab experience an IR, even in the setting of pre- and post-medication. In a study of daratumumab SC (also administered with pre- and post-medication), patients who received 1200 mg or 1800 mg of daratumumab SC had an IR incidence of 12.5% and 24.4%, respectively, significantly lower than the incidence seen with IV administration (15). In a healthy volunteer study of the anti-CD38 monoclonal antibody TAK-079, in which participants received maximum doses of 0.06 mg/kg IV and 0.6 mg/kg SC, no infusion reactions were reported (16). Two of 6 participants who received 0.6 mg/kg SC did have mild cytokine release syndrome, as demonstrated by minimal cytokine increases and the presence of mild clinical symptoms (headache, dizziness, and chills). Of note, no pre-medication or post-medication to prevent or reduce the incidence of infusion reactions was administered in that study.

Preliminary data for the incidence of infusion reactions for isatuximab SC is available from protocol TCD15484. As of March 2020, 11 participants with RRMM have completed the first cycle of isatuximab 1000 mg SC in combination with pomalidomide (1 cycle consists of 4 weekly isatuximab injections). Among these patients, there was only a single recorded infusion reaction (graded as mild), which occurred with the first infusion.

Overall, the available data for anti-CD38 antibodies suggest that infusion reactions occur less frequently when the antibody is administered subcutaneously and at low doses. In this study, participants will receive pre-medication before the first two administrations of isatuximab. Participants may also receive these medications prior to subsequent doses if deemed necessary by the Investigator, in consultation with the Sponsor.

### 2.3.2 Infections, COVID-19, and other risks

While plasma cells can produce pathogenic autoantibodies, they also produce protective antibodies, such as those that emerge following infection or vaccination. By depleting plasma cells, isatuximab has the potential to increase the risk of infection, although conclusions in this regard from RRMM studies are difficult as RRMM patients have an inherently increased risk of infection. Data collected from the use of the anti-CD38 monoclonal antibody daratumumab in the setting of RRMM has been conflicting. In one study with 30 RRMM patients, 4 weeks of daratumumab therapy did not significantly alter the levels of polyclonal IgG, although levels of IgA, IgM, and IgE did significantly decline (17). Additionally, 17 RRMM patients were vaccinated against *S. pneumoniae* and *H. influenzae* Type B during daratumumab therapy and had response rates similar to that of RRMM patients not treated with daratumumab (17). In another study, significant rates of hypogammaglobulinemia, a known risk factor for infection, were seen, and occurred as early as 4 weeks after the start of daratumumab in some patients (18 and communication with author). Internal data with isatuximab in RRMM patients has shown that patients with non-IgG myelomas treated with isatuximab for 6 months did not have significant declines in overall IgG levels, although IgA levels declined in patients with IgG myelomas. The effect of isatuximab on the production of anti-infective antibodies therefore remains uncertain.

If isatuximab does in fact decrease levels of antiviral antibodies, participants infected with SARS-CoV-2 during isatuximab treatment may experience a longer or more severe infection, or may not generate protective antibodies as a result of infection. Testing for SARS-CoV-2 infection during screening will be determined by the Investigators and Sponsor based on local guidelines and COVID-19 prevalence at each site. Participants known to have had COVID-19 prior to study entry must be fully recovered in order to be eligible for participation. Participants enrolled in the study will be counseled to avoid situations that may place them at increased risk for COVID-19. If a patient is diagnosed with COVID-19 during the study, isatuximab will be discontinued. If the participant is asymptomatic but has a positive SARS-CoV-2 test, the decision regarding discontinuation will be made by the Investigator in consultation with the Sponsor. Once the patient is fully recovered, the decision to restart treatment will be made by the Investigator and Sponsor.

The effect of isatuximab on vaccination responses is unknown. By targeting plasma cells, isatuximab may interfere with vaccine-elicited immune responses. However, a series of RRMM patients who received vaccinations against *S. pneumoniae*, *H. influenzae* type B, and seasonal influenza during daratumumab treatment produced protective IgG antibody titers (17). Thus, vaccination during isatuximab treatment may indeed elicit protective titers. Antibody titers for common vaccines will be measured before, during, and after isatuximab therapy. While SARS-CoV-2 vaccination may be administered at any time during the study, it is recommended that the final vaccine dose be administered at least 2 weeks prior to the first dose of isatuximab, or that the vaccine be administered 30 days or more after the final dose of isatuximab.

CD38 is expressed on other lymphoid and myeloid cells, but at densities lower than plasma cells. Isatuximab could affect these cell populations as well. Modulation of such cells could increase the risk of infection and the risk of malignancies. A higher rate of secondary primary malignancies was observed in multiple myeloma patients who received isatuximab, pomalidomide, and dexamethasone as compared to those who received pomalidomide and dexamethasone alone.

However, the rate of secondary malignancies among patients who received isatuximab was not higher than the background rate in multiple myeloma patients.

Based on its mechanism of action, isatuximab can cause fetal harm when administered to a pregnant woman by causing fetal immune cell depletion and decreased bone density.

Isatuximab may cause neutropenia. Higher rates of neutropenia and febrile neutropenia were observed in multiple myeloma patients treated with isatuximab, pomalidomide, and dexamethasone as compared to those who received pomalidomide and dexamethasone alone.

RBCs express CD38, but at significantly lower density than plasma cells. Worsening of anemia is not expected, and anemia was not reported in healthy volunteers who received the anti-CD38 monoclonal antibody TAK-079 (16). Because isatuximab binds to CD38 found on red blood cells, it may interfere with routine blood bank compatibility testing and cross-matching, resulting in a false-positive indirect Coombs test. This interference is limited to the minor blood groups.

Isatuximab may also interfere with serum protein electrophoresis and immunofixation tests.

More detailed information about the known and expected benefits and risks and reasonably expected adverse events of isatuximab may be found in the Investigator's Brochure and package insert.

### 2.3.3 Risk assessment

**Table 1 - Risk assessment**

Potential risk of clinical significance	Summary of data/rationale for risk	Mitigation strategy
Infusion reactions	Infusion reactions are a common side effect of anti-CD38 monoclonal antibodies. However, these reactions appear to occur less frequently with subcutaneous administration and at lower doses.	Pre-medication for infusion reactions with diphenhydramine, famotidine, acetaminophen/paracetamol, and montelukast will be given prior to the first two administrations of isatuximab. Steroids (in addition to what the participant is already taking for wAIHA) will not be administered as such administration could confound the efficacy analysis. If an investigator wishes to continue pre-medication after the second isatuximab dose, this may be performed in consultation with the Sponsor.
Infection	Isatuximab may increase the risk of infection by depleting immune cells, particularly plasma cells, which produce antibodies. Data for the risk of infection with isatuximab derives primarily from multiple myeloma patients, who are at increased risk of infection as a result of their disease.	Serum immunoglobulin levels will be checked at screening and monitored throughout the study to detect instances of hypogammaglobulinemia. Participants with hypogammaglobulinemia may be treated with IVIg as per the investigator's discretion.

Potential risk of clinical significance	Summary of data/rationale for risk	Mitigation strategy
COVID-19	Isatuximab may decrease levels of antiviral antibodies and result in more severe infection, or prevent the development of immunity following infection.	The need for SARS-CoV-2 testing during screening will be determined by the Sponsor and the Investigators at each site. Participants will be counseled to avoid situations that may place them at increased risk for COVID-19. If a patient is diagnosed with SARS-CoV-2 during the study, isatuximab will be at least temporarily discontinued. If the participant is asymptomatic but has a positive SARS-CoV-2 test, the decision regarding discontinuation will be made by the Investigator in consultation with the Sponsor.
Embryo-fetal toxicity	Isatuximab can cause fetal harm when administered to a pregnant woman by causing fetal immune cell depletion and decreased bone density.	WOCBP are required to use contraception during the study and for 5 months after the last isatuximab dose. Pregnancy testing will be performed every 4 weeks during the study.
Neutropenia	Isatuximab may cause neutropenia	Complete blood counts will be monitored throughout the study.
Malignancy	Secondary malignancies were observed following isatuximab treatment in multiple myeloma patients	Patients will undergo clinical assessments for 14 weeks after the last isatuximab dose. Of note, patients with multiple myeloma have an increased rate of secondary malignancies, and isatuximab does not appear to increase this rate above background levels. Additionally, there is no evidence of an elevated risk of malignancies among wAIHA patients.
Interference with laboratory tests	Isatuximab may cause a false-positive indirect Coombs test and may interfere with serum protein electrophoresis and immunofixation tests	Blood typing will be performed prior to isatuximab dosing if not previously obtained within the past 1 month.

### 2.3.4 Benefit assessment

Individuals with wAIHA who are refractory to current therapies have substantial morbidity associated with their disease, including fatigue, exertional dyspnea, thromboembolism, and the need for frequent blood transfusions. Severe cases can be life-threatening. Treatment with isatuximab may improve hemoglobin levels and possibly resolve anemia in these individuals, resulting in sustained improvements in quality of life and potential long-term treatment-free remission.

### **2.3.5 Overall benefit: risk conclusion**

Considering the measures taken to minimize risk to participants participating in this study, the potential risks identified in association with isatuximab are justified by the anticipated benefits that may be afforded to participants with wAIHA.

### 3 OBJECTIVES AND ENDPOINTS

**Table 2 - Objectives and endpoints**

Objectives	Endpoints
Primary	

• Part A: To evaluate the safety and tolerability of subcutaneous injections of isatuximab in adults with wAIHA.

• Part B: To evaluate the efficacy of the selected dose in adults with wAIHA.

 
• Standard clinical and laboratory parameters and adverse events.
 
• Overall response rate (response (R) or complete response (CR)) at Day 85.
 
R is defined as an increase in hemoglobin by <math>\geq 2</math> g/dL from baseline and an absence of transfusion in the last 7 days and absence of rescue medications in the past 4 weeks. Biochemical evidence of hemolysis may still be present.
 
CR is defined as hemoglobin <math>\geq 11</math> g/dL (women) or <math>\geq 12</math> g/dL (men), no evidence of hemolysis (normal bilirubin, LDH, haptoglobin, and reticulocytes), and absence of transfusion in the last 7 days and absence of rescue medication in the past 4 weeks.

Secondary	
Part A (Cohorts 2 and 3 only)	

• To evaluate the efficacy of isatuximab in adults with wAIHA.

• Overall response rate (response (R) or complete response (CR)) at Day 85.

R is defined as an increase in hemoglobin by <math>\geq 2</math> g/dL from baseline and an absence of transfusion in the last 7 days and absence of rescue medications in the past 4 weeks. Biochemical evidence of hemolysis may still be present.

CR is defined as hemoglobin <math>\geq 11</math> g/dL (women) or <math>\geq 12</math> g/dL (men), no evidence of hemolysis (normal bilirubin, LDH, haptoglobin, and reticulocytes), and absence of transfusion in the last 7 days and absence of rescue medication in the past 4 weeks.

• Proportion of participants with durable hemoglobin response by Day 169. Durable response is defined as Hb level <math>\geq 10</math> g/dL with an increase from baseline of <math>\geq 2</math> g/dL on three consecutive evaluable visits during the study period; with absence of transfusion and no rescue medication during the period of 3 consecutive visits and for at least 7 days (transfusions) and 4 weeks (rescue medication) prior to the first consecutive visit.

• Overall response rate at Day 169, median time to R or CR, median time to loss of R or CR (loss of R defined as hemoglobin <math>< 10</math> g/dL at two consecutive visits at least 7 days apart and initiation of new treatment for anemia or increase in steroid dose; loss of CR is defined as hemoglobin <math>< 11</math> g/dL (women) or <math>< 12</math> g/dL (men) at two consecutive visits at least 7 days apart), proportion of participants requiring rescue therapy (any wAIHA-directed therapy other than prednisone or transfusion) or splenectomy.

Objectives	Endpoints

 
To evaluate the impact of isatuximab treatment on fatigue.
 
 
Part B
 
 
To evaluate the safety and tolerability of isatuximab in adults with wAIHA.
 
To evaluate the durability of response to isatuximab and time to response.
 
	
 
FACIT-fatigue scale score at Day 85 and Day 169.
 


 
To evaluate the impact of isatuximab treatment on fatigue.
 
 
Parts A (all Cohorts) and B
 
 
To evaluate the effect of isatuximab on markers of hemolysis.
 
To characterize the pharmacokinetic profile of isatuximab in adults with wAIHA.
 
To evaluate the immunogenicity of isatuximab.
 
	
 
Standard clinical and laboratory parameters and adverse events.
 
Proportion of participants with durable hemoglobin response by Day 169. Durable response is defined as Hb level <math>\geq 10</math> g/dL with an increase from baseline of <math>\geq 2</math> g/dL on three consecutive evaluable visits during the study period; with absence of transfusion and no rescue medication during the period of 3 consecutive visits and for at least 7 days (transfusions) and 4 weeks (rescue medication) prior to the first consecutive visit.
 
Overall response rate at Day 169, median time to R or CR, median time to loss of R or CR (loss of R defined as hemoglobin <math>< 10</math> g/dL at two consecutive visits at least 7 days apart and initiation of new treatment for anemia or increase in steroid dose; loss of CR is defined as hemoglobin <math>< 11</math> g/dL (women) or <math>< 12</math> g/dL (men) at two consecutive visits at least 7 days apart), proportion of participants requiring rescue therapy (any wAIHA-directed therapy other than prednisone or transfusion) or splenectomy.
 
FACIT-fatigue scale score at Day 85 and Day 169.
 

Tertiary/Exploratory	
Parts A (all Cohorts) and B	
 
Change from baseline in LDH, haptoglobin, reticulocytes, and total bilirubin at 1, 2, 4, 8, 12, and 24 weeks.
 
PK parameters after subcutaneous administrations (including <math>C_{max}</math> and <math>AUC_{0-2\text{ week}}</math>).
 
Incidence and titer (if relevant) of anti-isatuximab antibodies.
 

Objectives	Endpoints

To describe the effect of isatuximab on bone marrow plasma cells, particularly those producing anti-RBC antibodies.

	

Levels of plasma cells from bone marrow biopsy in participants who have a biopsy/aspirate performed.

Part B only	

To investigate the effect of isatuximab on quality of life

Change in the following assessments: Patient Global Impression of Change (PGIC), Patient Global Impression of Severity (PGIS), Clinical Global Impression of Efficacy (CGI-E), Clinical Global Impression of Improvement (CGI-I), Clinical Global Impression of Severity (CGI-S)

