#### Type of participant and disease characteristics

I 02. Males and females with a confirmed diagnosis of primary wAIHA or systemic lupus erythematosus (SLE)-associated wAIHA (without other SLE-related manifestations apart from cutaneous and musculoskeletal manifestations) who meet the following criteria:

- a) Hemoglobin level  $<10$  g/dL at Screening.
- b) Hemolysis (haptoglobin  $\leq 40$  mg/dL and total or indirect/unconjugated bilirubin above the upper limit of normal).
- c) Positive direct antiglobulin test (DAT) (IgG or IgG + complement C3d pattern or IgM warm autoantibodies [positive dual DAT]).

I 03. Participants who have previously failed to maintain a sustained response after treatment with corticosteroids (corticosteroid-refractory or corticosteroid-dependent primary wAIHA).

I 04. Part A only: Participants who have previously failed to maintain a sustained response after treatment with rituximab (or other anti-CD20 monoclonal antibodies). The last dose of the anti-CD20 antibody must have been administered at least 12 weeks before enrollment.

Part B: Participants who have had an insufficient response to at least 1 prior therapy in addition to corticosteroids (splenectomy is regarded as a prior therapy).

Note: For criteria specific to participants enrolled in France, see Appendix 7 ([Section 10.7](#))

I 05. Eastern Cooperative Oncology Group (ECOG) performance status Grade 2 or lower.

I 06. Up-to-date vaccination status as per local guidelines.

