### **Prior/concomitant therapy**

E 16. Receipt of live vaccine(s) within 3 months prior to enrollment.

- E 17. Concurrent treatment with corticosteroids, unless the participant has been on a stable daily dose for  $\geq 15$  days prior to enrollment.
- E 18. Concurrent treatment with erythropoietin, unless the patient has been on a stable dose for 3 months prior to enrollment.
- E 19. Concurrent use of iron supplementation, unless the patient has been on a stable dose for  $\geq 30$  days prior to enrollment.
- E 20. Treatment with cyclophosphamide within 4 weeks prior to enrollment.
- E 21. Treatment with cytotoxic drugs (other than cyclophosphamide) within 12 weeks prior to enrollment.
- E 22. Treatment with non-cytotoxic, immunomodulatory drugs (including but not limited to Cyclosporine, Sirolimus, Tacrolimus, Idelalisib, Ibrutinib), excluding biologic agents, within 4 weeks prior to enrollment.
- E 23. Treatment with any biologic agent within 12 weeks prior to enrollment.
- E 24. Use of prescribed or over-the-counter medications, supplements, vitamins, and/or herbal remedies within 2 weeks before enrollment which, in the judgment of the Investigator, may adversely affect the participant's welfare or the integrity of the study results.

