### **6.5.1 Rescue therapy**

The use of rescue medications is allowable during the study. The date and time of rescue medicine as well as the name and dosage regimen of the rescue medication/intervention must be recorded.

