The proportion of participants requiring rescue therapy (any wAIHA-directed therapy other than prednisone or transfusion) or splenectomy will also be described by dose level group.

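### In Part A Cohorts 2 and 3, the response definitions screen rescue medication for only 4 weeks and do not name splenectomy, so a response that follows either can be credited to isatuximab

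*Protocol*

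**What the plan says.** **Response definitions (Protocol Table 2).** R requires a hemoglobin rise of at least 2 g/dL together with "an absence of transfusion in the last 7 days and absence of rescue medications in the past 4 weeks". CR adds hemoglobin and hemolysis thresholds and carries the same two look-backs. Durable response requires no transfusion or rescue medication across its three consecutive visits and "for at least 7 days (transfusions) and 4 weeks (rescue medication) prior to the first consecutive visit".

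**Rescue (Protocol 6.5.1).** "The use of rescue medications is allowable during the study". No limit is set on class or timing. Rescue is not listed in Protocol 7.1.1 as a reason to stop study drug, and participants who do stop are still followed.

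**Splenectomy.** It appears in a separate endpoint, the "proportion of participants requiring rescue therapy (any wAIHA-directed therapy other than prednisone or transfusion) or splenectomy". It stands there beside rescue therapy and not within it. None of the definitions of R, CR or durable response mentions it. Inclusion criterion I 04 counts it as a prior therapy for Part B.

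**Non-response rule (Protocol 9.4.2.2 and 9.4.3.1.1).** Only a response that cannot be evaluated is set to non-response.

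**Entry windows (Protocol 5.1 and 5.2).** I 04, Part A: "The last dose of the anti-CD20 antibody must have been administered at least 12 weeks before enrollment". E 23 excludes "Treatment with any biologic agent within 12 weeks prior to enrollment". E 21 excludes "Treatment with cytotoxic drugs (other than cyclophosphamide) within 12 weeks prior to enrollment". E 20 (cyclophosphamide) and E 22 (non-cytotoxic immunomodulators other than biologics) use 4 weeks.

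**SAP.** Section 1.2 drops Part B and several other analyses. It does not change the Part A response analyses and adds no rule for rescue or splenectomy.

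**The concern.** The stated aims for Cohorts 2 and 3 are the efficacy of isatuximab and the durability of its response. In an open-label, single-arm study of previously treated patients, those most likely to receive a further wAIHA therapy or a splenectomy are those in whom isatuximab is not working. Such a participant stays in follow-up and stays evaluable. If the rescue was given early enough, or was surgical, a later hemoglobin rise satisfies R, CR or durable response, and the response rate credits it to isatuximab. There is no control arm in which the same thing would happen and become visible. With Part B not performed, these rates are the main efficacy result the trial will report.

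**Working it through.** **1. The plan's own interval.** Protocol Table 6 gives Clopper-Pearson limits at a 50% response rate. With x responders of n, the lower limit is the 0.025 quantile of Beta(x, n−x+1) and the upper limit is the 0.975 quantile of Beta(x+1, n−x). For x = 7, n = 14 this gives 0.230 to 0.770, half-width (0.770 − 0.230)/2 = 0.270, as printed. The other three rows also reproduce. No figure in the table is disputed; it only fixes the method used in step 6.

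**2. How far the look-back reaches.** For a visit on Day V and a look-back of L days, screening starts at Day V − L, and V − L − 1 of the V − 1 days since Day 1 are unscreened.

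| Visit | Look-back | Screened from | Unscreened days |
|---|---|---|---|
| Day 85 | 28 days (4 weeks) | 85 − 28 = Day 57 | 56 of 84 (67%) |
| Day 85 | 84 days (12 weeks) | 85 − 84 = Day 1 | 0 of 84 (0%) |
| Day 169 | 28 days | 169 − 28 = Day 141 | 140 of 168 (83%) |
| Day 169 | 84 days | 169 − 84 = Day 85 | 84 of 168 (50%) |

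The protocol does not say whether the boundary day itself counts, so these days are approximate. The percentages are shares of calendar time, not estimates of bias.

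**3. Durable response.** If the three visits are Days 57, 71 and 85, the look-back starts at 57 − 28 = Day 29. Rescue before about Day 29 does not bar a durable response.

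**4. Comparison with the entry windows.**

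| Therapy | Entry window | Look-back in R and CR |
|---|---|---|
| Anti-CD20 antibody (I 04) | 12 weeks | 4 weeks |
| Any biologic (E 23) | 12 weeks | 4 weeks |
| Cytotoxic other than cyclophosphamide (E 21) | 12 weeks | 4 weeks |
| Cyclophosphamide (E 20) | 4 weeks | 4 weeks |
| Non-cytotoxic immunomodulator (E 22) | 4 weeks | 4 weeks |
| Splenectomy | none | not named |

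The windows differ in the first three rows and agree in the next two.

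**5. Two cases run through the text.**
- A participant receives a rescue biologic on Day 50 and meets the hemoglobin criterion on Day 85. The gap is 85 − 50 = 35 days, more than 28, so R is allowed. It is less than 84, so the same gap before enrollment would have excluded the person under E 23.
- A participant has a splenectomy on Day 90 and meets the hemoglobin and hemolysis criteria on Day 169, with no transfusion or other rescue in the windows. The gap is 169 − 90 = 79 days. CR is allowed. Protocol 6.5.1 mentions an intervention beside medication when it lists what to record. If surgery is read into the rescue clause on that ground, 79 days still lies outside the 28-day window.

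**6. Effect of one such participant.** With 3 planned per cohort, one reclassification moves the rate by 1/3 = 33.3 points: for example from 2/3 (exact 95% CI 0.094 to 0.992) to 1/3 (0.008 to 0.906). In the planned set of 14 it would have been 1/14 = 7.1 points. The documents give no rate of rescue or splenectomy, so the number affected could be anything from none to all responders.

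**The case against.** Much of the case on the other side stands.

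- **The 4 weeks were chosen deliberately.** Protocol 3.1 bases the endpoints on consensus guidelines, and the amendment history gives alignment with other wAIHA studies as the reason for the clause. Comparability is a fair reason to keep it.
- **Entry windows need not match an endpoint look-back.** A reader might infer that the protocol regards these drugs as active for 12 weeks and so contradicts itself. The documents do not support that. No reason is given for the windows, and nearby 3-month windows for live vaccines and serious infection make a safety purpose equally possible. Nor does the mismatch cover all rescue, since E 20 and E 22 already agree with the look-back.
- **Rituximab is a weak illustration.** Part A participants had already failed to maintain a response to an anti-CD20 antibody, so the rituximab response figures in Protocol 2.2 do not carry over to them.
- **Attribution is mixed.** Isatuximab is dosed through Day 71, so rescue before Day 57 overlaps treatment. A later response is not necessarily due to the rescue.
- **Affected cases can be found.** Rescue or splenectomy is reported by dose group, response is shown by visit, and response data are listed. The rate itself would still count these participants as responders.
- **The SAP follows the early stop.** Replacing the protocol's medication rule as the basis for conclusions at that stage would be post hoc. This argues for a supportive row rather than a new main definition.

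**Conclusion.** The gap is real, and no rule in either document closes it. Rescue medication before about Day 57 or about Day 141 is unscreened for R and CR at Day 85 and Day 169 respectively, and splenectomy is not named at all; on the most generous reading only the last 4 weeks would count. Responses that follow a splenectomy or a long-acting rescue drug can therefore enter the isatuximab response rate. Compared with a rule that counts any on-study rescue as non-response, the present rule can only give the same rate or a higher one.

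A reader might go further and conclude that the reported rates are inflated. That cannot be said: without a rescue rate the size of the effect is unknown and may be zero. What can be said is that one case shifts a cohort of 3 by 33 points. The planned size of 3 is assumed throughout. The endpoints are descriptive, with no formal test, so this is a matter of how the result is presented and interpreted. It still deserves a change, because these are the efficacy figures that remain.

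**What to change.** Analysis only, in SAP 1.2, for Part A Cohorts 2 and 3:

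1. State that a participant who has a splenectomy after Day 1 is a non-responder for R, CR and durable response at every later visit.
2. Keep the protocol's 4-week rule for rescue medication as the main row. Add a supportive row in which any rescue therapy or splenectomy since Day 1 counts as non-response at later visits. Take rescue therapy as Protocol 9.4.3.1.1 already describes it, for participants "requiring rescue therapy (any wAIHA-directed therapy other than prednisone or transfusion) or splenectomy".
3. Flag these participants in the response listing. Where the two rows differ, say so in the efficacy and durability conclusions.

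Borrowing the 12-week entry windows as the look-back is not enough: half the period would remain unscreened at Day 169, and nothing would change for E 20 and E 22 drugs.

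**Cost.** SAP wording and one extra row. Names and dates of concomitant and rescue treatment are already recorded under Protocol 6.5 and 6.5.1. The response rate may fall by 33 points per affected participant in a cohort of 3. The supportive row is conservative for someone rescued early who later responds to isatuximab, which is why it supplements the main row and does not replace it.
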